8.1.1 Adverse (Drug) Reaction

All noxious and unintended responses to a medicinal product related to any dose should be considered an adverse drug reaction. “Responses” to a medicinal product means that a causal relationship between a medicinal product and an AE is at least a reasonable possibility (i.e., the relationship cannot be ruled out).

8.1.2 Unexpected Adverse Drug Reaction

An Unexpected Adverse Drug Reaction is defined as an adverse reaction, the nature or severity of which is not consistent with the applicable product information.

8.1.3 Assessment of Adverse Events by the Investigator

The Investigator will assess the severity (intensity) of each AE using the CTCAE version 5.0 and will also categorize each AE as to its potential relationship to study drug using the categories of “no” or “yes.”

Severity assessment

The severity of all AEs should be graded according to the CTCAE version 5.0. For those AE terms not listed in the CTCAE, the following grading system should be used:

- CTCAE Grade 1: Mild; asymptomatic or mild symptoms; clinical or diagnostic observations only; intervention not indicated;
- CTCAE Grade 2: Moderate; minimal local or noninvasive intervention indicated; limiting age-appropriate instrumental activities of daily living;
- CTCAE Grade 3: Severe or medically significant but not immediately life-threatening; hospitalization or prolongation of hospitalization indicated; disabling; limiting self-care activities of daily living;
- CTCAE Grade 4: Life threatening consequences; urgent intervention indicated; and
- CTCAE Grade 5: Death related to the AE.

Causality assessment

The relationship of an AE to the administration of the study drug is to be assessed according to the following definitions:

- No (unrelated, not related, or unlikely to be related) – The time course between the administration of study drug and the occurrence or worsening of the AE rules out a causal

relationship and another cause (e.g., concomitant drugs, therapies, complication) is suspected; or

- Yes (possibly related, probably related, or definitely related) – The time course between the administration of study drug and the occurrence or worsening of the AE is consistent with a causal relationship and no other cause (e.g., concomitant drugs, therapies, complications) can be identified. The definition implies a reasonable possibility of a causal relationship between the event and the study drug. This means that there are facts (evidence) or arguments to suggest a causal relationship.

The following factors should also be considered when assessing the relationship of an AE to the study drug:

- The temporal sequence from study drug administration;
The event should occur after the study drug is given. The length of time from study drug exposure to event should be evaluated in the clinical context of the event.
- Underlying, concomitant, intercurrent diseases;
Each report should be evaluated in the context of the natural history and course of the disease being treated and any other disease the subject may have.
- Concomitant drugs;
The other drugs the subject is taking or the treatment the subject receives should be examined to determine whether any of them might be recognized to cause the event in question.
- Known response pattern for this class of study drug;
Clinical and/or preclinical data may indicate whether a particular response is likely to be a class effect.
- Exposure to physical and/or mental stresses; and
The exposure to stress might induce adverse changes in the recipient and provide a logical and better explanation for the event.
- The pharmacology and PK of the study drug.
The known pharmacologic properties (absorption, distribution, metabolism, and excretion) of the study drug should be considered.

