Note: Events related to progression of the subject's underlying COVID-19 diagnosis will be captured as endpoints; therefore, events clearly related to progression of the subject's underlying COVID-19 (signs or symptoms of progression) should not be reported as an SAE unless considered related to study drug or if the outcome is fatal during the clinical trial or within the safety reporting period. If the event has a fatal outcome during that timeframe, the event of "Progression of COVID-19" must be recorded as an SAE with a fatal outcome.

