#### *3.6.1 Adverse Events (AEs)*

AEs will be captured from the date of informed consent through study completion. All AEs will be coded to system organ class and preferred term using MedDRA version 23.1.

Treatment-emergent adverse events (TEAEs) are defined as AEs that start after the first dose of study drug. AEs with partially missing onset dates will also be included as treatment emergent when the month (if it exists) and the year occur on or later than the month and year of the first dose date.

An overview of AEs will be provided including counts and percentages of subjects (and event counts) with the following:

- Any TEAEs (overall and by maximum severity)

- Any study drug related TEAEs
- Any serious AEs (SAEs)
- Any treatment-emergent serious AEs (TESEAEs)
- Any TEAEs leading to discontinuation of study drug
- Any AEs leading to death

Counts and percentages of subjects (and event counts) will also be presented by system organ class and preferred term for each of the categories in the overview.

Listings will be presented for all AEs and hospitalization data.

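### The Yes and No causality definitions in Protocol 8.1.3 are not complementary and conflict with the reasonable-possibility standard in 8.1.1, so some adverse events have no category

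*Protocol*

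**What the plan says.** Protocol 8.1.3 has two categories and no third option.

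- **No** has a timing part, "The time course between the administration of study drug and the occurrence or worsening of the AE rules out a causal" link, and a second part under which some alternative explanation must be suspected. Both parts are required. Its label also takes in events judged unlikely to be related.
- **Yes** applies when the timing "is consistent with a causal relationship and no other cause (e.g., concomitant drugs, therapies, complications) can be identified". Again both parts are required.

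The Yes bullet also carries weaker language. Its label reads "Yes (possibly related, probably related, or definitely related"), and its explanation says "The definition implies a reasonable possibility of a causal relationship between the event and the study drug". Protocol 8.1.1 defines an adverse drug reaction as a response for which a causal relationship "is at least a reasonable possibility (i.e., the relationship cannot be ruled out").

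The call is used in four places:

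- Protocol 9.2.2 tabulates events by relationship to study drug.
- SAP 3.6.1 has an overview row, "Any study drug related TEAEs", with a matching table by system organ class and preferred term.
- Protocol 8.2 says that events clearly due to COVID-19 progression "should not be reported as an SAE unless considered related to study drug or if the outcome is fatal".
- Protocol 8.3 makes SAE reporting after the 30-day window depend on the investigator considering the event related.

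**The concern.** A forced two-way call needs definitions that between them cover every event once. These do not, and the event left out is an ordinary one: it begins on study drug at a plausible time, and COVID-19 or a concomitant treatment could also explain it. Protocol 3.1 gives all subjects standard of care for COVID-19, so an alternative explanation will often be available.

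An investigator facing such an event can follow the strict condition and decline Yes, or follow the explanatory sentence and 8.1.1 and choose Yes. Both have textual support. Safety is the primary endpoint, and the related-event tables are part of its analysis. The consequence for SAE reporting matters more, because a summary of all TEAEs cannot restore an SAE that was never reported as one.

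**Working it through.** The documents state no figure on this point, so there is none to reproduce. The check is logical, with one illustrative calculation.

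**1. Coverage.** Cross the two conditions that 8.1.3 uses, treating a suspected cause and an identified cause as the same thing.

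| Timing | Other cause | Meets Yes? | Meets No? | Category |
|---|---|---|---|---|
| Compatible | Absent | yes | no | Yes |
| Compatible | Present | no | no | none |
| Excludes the drug | Present | no | yes | No |
| Excludes the drug | Absent | no | no | none |

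Two of four combinations have no category.

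**2. Does this depend on equating suspected with identified?** Allow three levels of other cause (none, suspected only, identified), giving 2 × 3 = 6 combinations. Compatible timing with a merely suspected cause then becomes Yes. Compatible timing with an identified cause still has no category, and neither does excluded timing with no other cause. That leaves 2 of 6 uncovered. The important gap narrows but remains.

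**3. Conflict of standards.** Take an event with compatible timing and another identifiable cause, where a drug contribution cannot be excluded. Under 8.1.1 it is an adverse drug reaction. Under the explanatory sentence in the Yes bullet it is a reasonable possibility, hence Yes. Under the strict condition in that same bullet it is not Yes.

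**4. The progression exception.** Protocol 8.2 keeps non-fatal COVID-19 progression out of SAE reporting unless it is considered related. An event clearly due to progression already has another cause. If the strict condition is applied to the letter, such an event cannot be called related and the exception cannot operate. The SAE and treatment-emergent SAE rows in SAP 3.6.1 inherit that result for these events.

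**5. Illustration of size.** About 30 subjects randomised 2:1 gives 30 × 2/3 = 20 on ADX-629. Let p be the share of subjects with a truly drug-related event and q the share of those events that also have another cause. Neither value is in the documents. If every such event were entered as No, the chance that at least one subject is counted as related is 1 − (1 − p(1 − q))^20.

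| p | q = 0 | q = 50% | q = 75% | q = 90% |
|---|---|---|---|---|
| 10% | 88% | 64% | 40% | 18% |
| 20% | 99% | 88% | 64% | 33% |

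For example, with p = 10% and q = 50%: 1 − 0.95^20 = 0.64. The q = 0 column also gives the result if every ambiguous event were entered as Yes. The text allows anything from that column to the one that applies.

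**The case against.** The strongest reply is that 8.1.3 should be read as a whole. The label and explanation under Yes point to a low threshold. The list that follows treats underlying disease and concomitant drugs as factors to weigh, not as disqualifiers. A sensible investigator would choose Yes for a reasonable possibility. This stands as far as it goes: the section contradicts itself and does not impose one strict rule. It does not remove the contradiction, and the listed factors do not say that they override the definitions.

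A reader might go further and infer that almost no event in this trial could be counted as drug-related. The documents do not support that. The ambiguous event does not meet No either, because its timing does not exclude the drug, so the text does not send it to No. Near-total loss would also need nearly every related event to have another cause, and no rate is given.

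A reader might also infer that the primary safety evaluation is undermined. SAP 3.6.1 counts all TEAEs by arm and maximum severity, as well as SAEs, discontinuations and deaths, without regard to relatedness. Laboratory tests, vital signs, physical examinations and ECGs do not use the call. Calls are made blind (Protocol 5.3), so knowledge of the assigned arm should not distort them.

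On reporting, Protocol 8.3 requires all SAEs to be reported initially whatever their relationship, and fatal progression is always an SAE. The progression carve-out is limited to events clearly due to progression. Protocol 8.5 does not tie SUSARs to the 8.1.3 rule, and 8.1.1 defines a reaction broadly, so an effect on SUSAR reporting is not established.

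**Conclusion.** The point holds as an internal inconsistency that should be corrected. The Yes and No definitions leave two of four combinations without a category, and the strict Yes condition contradicts both its own bullet and 8.1.1. Measured against 8.1.1, related-TEAE counts may be understated, or may vary with which sentence an investigator follows. The same applies to reporting of non-fatal COVID-19 progression and of SAEs after the 30-day window.

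The size is unknown. The figures in the illustration rest on assumed values of p and q and on every ambiguous event being entered as No. They show that a loss could be material with about 20 treated subjects, not that it will occur. The second uncovered combination, excluded timing with no other suspected cause, completes the logic but is likely to matter less, since 8.1.1 would not treat such an event as a reaction. The comparison of all TEAEs between arms is not affected.

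**What to change.** Reconcile 8.1.3 with 8.1.1 so that every adverse event falls in exactly one category:

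1. Define Yes as a reasonable possibility that study drug caused or contributed to the event, whether or not another cause is also possible.
2. Define No as the exact complement: no such reasonable possibility.
3. Delete the condition under Yes that no other cause can be found, and the condition under No that another cause must be suspected. The first closes the compatible-timing gap and the second closes the excluded-timing gap.
4. Settle the label for events unlikely to be related. It now sits under No, yet an unlikely relationship has not necessarily been ruled out, which is the 8.1.1 wording. State on which side of the boundary it falls and use the same boundary in both sections.

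The list of factors to weigh can stay. The change is to wording in the protocol and eCRF completion guidance; the SAP tables keep their form. The cost is that more events will be classed as related, in both arms, so the related-TEAE row should be read against placebo. Any calls already made under the present text should be reassessed while still blinded.

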8.2 Serious Adverse Events

An AE or adverse reaction is considered serious if, in the view of either the Investigator or Sponsor, it results in any of the following outcomes:

- Death;
- A life-threatening AE;

Note: An AE or adverse reaction is considered “life-threatening” if, in view of either the Investigator or Sponsor, its occurrence places the subject at immediate risk of death. It does not include an event that, had it occurred in a more severe form, might have caused death.

- Requires hospitalization or prolongation of existing hospitalizations;

Note: Any hospital admission with at least 1 overnight stay will be considered an inpatient hospitalization. An emergency room or urgent care visit without hospital admission will not be recorded as a SAE under this criterion, nor will hospitalization for a procedure scheduled or planned before signing of informed consent, or elective treatment of a pre-existing condition that did not worsen from baseline. However, unexpected complications and/or prolongation of hospitalization that occur during elective surgery should be recorded as AEs and assessed for seriousness. Admission to the hospital for social or situational reasons (i.e., no place to stay, live too far away to come for hospital visits, respite care) will not be considered inpatient hospitalizations.

- A persistent or significant disability/incapacity or substantial disruption of the ability to conduct normal life functions;
- A congenital anomaly/birth defect; or
- An important medical event.

Note: Important medical events that do not meet any of the above criteria may be considered an SAE when, based upon appropriate medical judgment, they may jeopardize the subject and may require medical or surgical intervention to prevent 1 of the outcomes listed above. Examples of such medical events include allergic bronchospasm requiring intensive treatment in an emergency room or at home, blood dyscrasias or convulsions that do not result in inpatient hospitalizations, or the development of drug dependency.

Note: Events related to progression of the subject's underlying COVID-19 diagnosis will be captured as endpoints; therefore, events clearly related to progression of the subject's underlying COVID-19 (signs or symptoms of progression) should not be reported as an SAE unless considered related to study drug or if the outcome is fatal during the clinical trial or within the safety reporting period. If the event has a fatal outcome during that timeframe, the event of "Progression of COVID-19" must be recorded as an SAE with a fatal outcome.

8.3 Serious Adverse Event Reporting – Procedures for Investigators

Initial reports

All SAEs occurring from the time of informed consent must be reported to [REDACTED] Clinical Safety within 24 hours of the knowledge of the occurrence. After the 30-day reporting window, any SAE that the Investigator considers related to the study drug must be reported to the [REDACTED] Clinical Safety or the Sponsor/designee.

To report the SAE, complete the SAE form electronically in the electronic data capture (EDC) system for the clinical trial. When the form is completed, [REDACTED] Safety personnel will be notified electronically by the EDC system and will retrieve the form. If the event meets serious criteria and it is not possible to access the EDC system, [REDACTED]

[REDACTED] within 24 hours of awareness. When the EDC system becomes available, the SAE information must be entered within 24 hours of the system becoming available.

Follow-up reports

The Investigator must continue to follow the subject until the SAE has subsided or until the condition becomes chronic in nature, stabilizes (in the case of persistent impairment), or the subject dies.

Within 24 hours of receipt of follow-up information, the Investigator must update the SAE form electronically in the EDC system for the clinical trial and submit any supporting documentation (e.g., subject discharge summary or autopsy reports) to [REDACTED] Clinical Safety via fax or email. If it is not possible to access the EDC system, refer to the procedures outlined above for initial reporting of SAEs.

8.4 Pregnancy Reporting

If a subject becomes pregnant during the clinical trial or within the safety follow-up period defined in the protocol, the Investigator is to stop dosing with study drug(s) immediately and the subject should be withdrawn from the clinical trial. Early termination procedures should be implemented at that time.

A pregnancy is not considered to be an AE or SAE; however, it must be reported to [REDACTED] Clinical Safety within 24 hours of knowledge of the event. [REDACTED] Clinical Safety will then provide the Investigator/site the Exposure *In Utero* (EIU) form for completion. The Investigator/site must complete the EIU form and fax/email it back to [REDACTED] Clinical Safety.

If the female partner of a male subject becomes pregnant while the subject is receiving study drug or within the safety follow-up period defined in the protocol, the Investigator should notify [REDACTED] Clinical Safety as described above.

The pregnancy should be followed until the outcome of the pregnancy, whenever possible. Once the outcome of the pregnancy is known, the EIU form should be completed and faxed/mailed to [REDACTED] Clinical Safety. If the outcome of the pregnancy meets the criteria for immediate classification as an SAE (i.e., postpartum complication, spontaneous abortion, stillbirth, neonatal death, or congenital anomaly), the Investigator should follow the procedures for reporting an SAE.

8.5 Expedited Reporting

The Sponsor/designee will report all relevant information about Suspected Unexpected Serious Adverse Reactions (SUSARs) that are fatal or life-threatening as soon as possible to the FDA, but no later than 7 days after knowledge by the Sponsor/designee of such a case. Relevant follow-up information will subsequently be communicated within an additional 8 days.

All other SUSARs will be reported to the FDA as soon as possible but within a maximum of 15 days of first knowledge by the Sponsor/designee.

The Sponsor/designee will also report any additional expedited safety reports required in accordance with the timelines outlined in country-specific legislation.

The Sponsor/designee will also inform all Investigators as required per local regulations.

The requirements above refer to the requirements relating to investigational medicinal product.

8.6 Safety Contact Information

8.7 Clinical Laboratory Evaluations

All standard blood tests will be analyzed by the local laboratory. Blood samples will be collected and processed per institutional requirements and local processes.

Clinical laboratory tests are to be performed only if not done routinely as standard of care and only to the extent that the tests are missing to meet the clinical trial requirements. The Investigator will review laboratory values for those outside of the normal range and will be required to conduct clinically appropriate follow-up procedures. Clinical significance of the values outside of normal ranges will be assessed by the Investigator.

Clinical laboratory tests, including chemistry, hematology, coagulation parameters, and urinalyses, will be measured according to the timing specified in the Schedule of Procedures (Appendix A). For specifics of the analytes measured, see Appendix B.

8.8 Vital Signs

Vital signs will include temperature, heart rate, blood pressure, respiratory rate, and oxygen saturation. Vital signs will be collected BID, both times prior to dosing with ADX-629. On Day 1, vital signs will also be collected at 2, 4, 6, and 8 hours post the morning dose.

8.9 Physical Examinations

A full physical examination will be performed only at Screening. Full physical examination will include the following systems: dermatological, head/eyes/ears/nose/throat, respiratory, cardiovascular, musculoskeletal, neurological, abdominal, and general appearance.

A targeted physical examination, driven by the subject's signs and symptoms, will be performed at the remaining visits, as specified in the Schedule of Procedures (Appendix A).

8.10 Electrocardiograms

Twelve-lead ECGs will be performed at Screening or Day 1 (pre-dose), on Day 1 at 1 hour and 6 hours post-dose, and on Day 7. Whenever ECGs and blood samples are specified to be collected at the same time, ECGs will be obtained before the blood samples. ECGs should be obtained in digital format when possible and archived.

Subjects should be in a supine position for at least 10 minutes prior to the ECG measurement. The ECG measurements will include heart rate, RR-interval, PR-interval, QT-interval, QRS-complex, and QTcF.

8.11 SARS-CoV-2 Testing

SARS-CoV-2 testing may be performed at Screening if needed. The subject must have a documented, laboratory-confirmed SARS-CoV-2 infection, as determined by PCR or another

commercial or public health assay, and a confirmatory test for SARS-CoV-2 within 3 days (72 hours) of randomization to be included in the clinical trial. A verbal report of infection will not suffice. This will be performed at Screening only if a documented result is unavailable.

8.12 Other Safety Assessment

A chest X-ray will be collected at Screening. Subjects will be excluded from the clinical trial if there are significant infiltrates on chest X-ray (e.g., involving >50% of lung fields) at Screening as determined by the Investigator.

9 STATISTICS

9.1 Analysis Populations

The following analysis populations are defined for this clinical trial:

- Intent-to-Treat (ITT) Population: All randomized subjects;
- Safety Population: All randomized subjects who receive at least 1 dose of study drug;
- Per-Protocol Population: All subjects in the ITT Population without major protocol deviations; and
- PD Population: All subjects who have at least 1 PD measurement.

